3 OBJECTIVES AND ENDPOINTS

OBJECTIVES	ENDPOINTS	JUSTIFICATION FOR ENDPOINTS
Primary		
To demonstrate patient-reported improvement in processor design with the SONNET 3 (EAS) (EAS) Audio Processor (AP) compared to the existing AP.	At least 77% of participants will report improvement in processor design with SONNET 3 (EAS) (EAS) compared to the existing AP on the Design subsection of the Audio Processor Comparison Survey (APCS) at Visit 2.	Based on changes in size, weight, and earhook, we expect the majority of users to report improved design with SONNET 3 (EAS). Warren et al., 2019 ¹ compared useability of a novel AP to the existing design and found that, 77% of participants reported improvement in design. A mean score >3 (6-point Likert scale) on the APCS Design subsection will indicate agreement with improved design of SONNET 3 (EAS).
Secondary		
	Summary of patient-reported satisfaction ratings (6-point Likert scale) on subsections of the APCS with SONNET 3 (EAS) (EAS) at Visit 2.	The APCS includes the Bluetooth Pairing, Backwards Compatibility, and Parent Impressions subsections to assess different areas of SONNET 3 (EAS) (EAS) usability.
	Summary of audiologist-reported satisfaction ratings on subsections of the Audiologist Survey at enrollment conclusion.	The Audiologist Survey assesses the clinician perspective on usability improvements with SONNET 3 (EAS) (EAS).

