7 STUDY PROCEDURES AND SCHEDULE

7.1 STUDY PROCEDURES

7.1.1 STUDY SPECIFIC PROCEDURES

The following procedures will be performed during the study and will be documented for each participant enrolled:

- Informed consent: Site study personnel will review the IC form with potential participants and obtain signature prior to initiating study activities. Participants will be allowed to ask questions and may withdraw consent at any time.
- Parental/Legal Guardian permission: Site study personnel will review the parental permission form with the parents/legal guardians and obtain parental permission before starting study activities. Parents/guardians will be allowed to ask questions and may withdraw consent at any time.
- Assent: If required by the IRB, site study personnel will review the assent form with the potential participant and obtain assent before starting study activities. Potential participants will be allowed to ask questions and may withdraw assent at any time.

- Patient-Reported Outcomes:
 - Audio Processor Comparison Survey (APCS): Participants will complete the APCS at Visit 2. The APCS includes questions arranged into four subsections that assess user or parent satisfaction with design, Bluetooth pairing, and backwards compatibility with the SONNET 3 (EAS) compared to the existing audio processor. Responses are captured with a 6-point Likert scale, and responses from the Design subsection will be analyzed for the primary endpoint. Responses on all other subsections will be summarized for the secondary endpoint.
- Audiologist Outcomes:
 - Audiologist Survey: This custom survey assesses clinician impressions of device usability with SONNET 3 (EAS) compared to the existing models, SONNET/SONNET 2 (EAS). The survey features three subsections and responses are captured with a 6-point Likert scale. This survey will be completed by the audiologists upon conclusion of enrollment.

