10 STATISTICAL CONSIDERATIONS

10.1 STATISTICAL HYPOTHESES

Primary Endpoint:

At least 77% of participants will report improvement (mean score >3 on a 6-point Likert scale) in processor design with the SONNET 3 (EAS) compared to the existing audio processor on the Design subsection of the Audio Processor Comparison Survey (APCS) at Visit 2.

Secondary Endpoints:

1. Summary of patient-reported satisfaction rating (6-point Likert scale) on subsections of the Audio Processor Comparison Survey (APCS) with SONNET 3 (EAS) at Visit 2.
2. Summary of audiologist-reported satisfaction ratings on subsections of the Audiologist Survey at enrollment conclusion.

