10.2 SAMPLE SIZE

The sample size estimate is based on attaining adequate power to test the primary hypothesis that at least 77% of participants will report subjective improvement in audio processor design with SONNET 3 (EAS) over the existing processor based on a single survey. The hypothesis test is a one-sample, one-sided test of the proportion of participants reporting an average score of >3 on the Audio Processor Comparison Survey (APCS) compared to 77%, based on the clinical trial for the Cochlear Nucleus 7 audio processor, where an average of 77% of participants responded with greater than neutral agreement (>50 on a 100-point scale) on survey questions addressing satisfaction with improved comfort with the new audio processor. For the purpose of this sample size calculation, 77% will represent the desired participant response proportion.

A power analysis was conducted using a binomial two-proportion test with the package 'pwr' in R. Using a 95% confidence interval, a sample size of 20 participants would provide 85% probability of rejecting the null hypothesis (H_0 : 77%). Calculations are based on the following assumptions:

- Hypothesized proportion: H_0 : $p < 0.77$;
- Expected proportion: H_1 : $p \geq 0.77$
- Significance level = 0.05
- One-sided
- Effect size $h=0.36$

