10.4.2 ANALYSIS OF THE PRIMARY EFFECTIVENESS ENDPOINT

The proportion of participants reporting design superiority with SONNET 3 (EAS) on the APCS will be calculated for the primary endpoint. The participant's responses to the Design subsection questions will be averaged and the proportion of participants who rated >3 on average will be compared to the hypothesized proportion of 77%. The statistical hypothesis for the primary endpoint is defined as:

$$H_0: p < 0.77$$

$$H_1: p \geq 0.77$$

where p is the proportion of participants who responded with a mean score of >3.

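### The responder cut (mean Design score >3 on a 6-point scale) is not tied to the scale's neutral point; under 1-6 coding it counts averaged scores above 3 and up to the 3.5 midpoint as improvement

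*Combined protocol and SAP*

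**What the plan says.** The rule appears in Sections 1.1, 3, 10.1, 10.2 and 10.4.2. Section 10.1 states that at least 77% of participants "will report improvement (mean score >3 on a 6-point Likert scale) in processor design". Section 3 gives the meaning of the cut: "A mean score >3 (6-point Likert scale) on the APCS Design subsection will indicate agreement with improved design of SONNET 3 (EAS"). Section 10.4.2 uses stronger wording: "The proportion of participants reporting design superiority with SONNET 3 (EAS) on the APCS will be calculated for the primary endpoint".

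The score is a within-participant average. Under Section 10.4.2 the "responses to the Design subsection questions will be averaged and the proportion of participants who rated >3 on average" is compared with 77%.

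The 77% comes from a published trial of another manufacturer's processor. Section 10.2 says its participants "responded with greater than neutral agreement (>50 on a 100-point scale") on questions about comfort, and that the figure is an average.

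On the instrument, Section 7.1.1 says only: "Responses are captured with a 6-point Likert scale, and responses from the Design subsection will be analyzed for the primary endpoint". Section 3 fixes the direction (a higher score means more agreement). No section gives the numeric coding, the anchors, a neutral point or the number of Design items, and the survey form is not among the documents.

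**The concern.** The benchmark rule is anchored at neutral. The trial's rule is anchored at the number 3, and whether 3 is neutral depends on a coding that the plan does not state. A 6-point scale has no middle category, so its midpoint falls between two answers.

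Under 1-6 coding, >3 selects exactly the favourable half of a single item. Once several items are averaged, means between 3 and 3.5 become possible. A participant whose answers lie mostly on the unfavourable side can then be reported as finding the new design superior, and the resulting proportion is set against a benchmark that excluded such answers.

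What is at stake is mainly the reported responder rate. Sections 2.3.2 and 2.2.3 (the risk-benefit assessment) say the results are meant to inform labeling and insurance coverage.

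**Working it through.** **Inputs from the documents.** Cut: mean >3 on a 6-point scale (Sections 3, 10.1, 10.4.2). Benchmark rule: >50 on a 100-point scale (10.2). Target 0.77, n = 20, one-sided, alpha 0.05 (10.2). No figure in the plan bears on where the cut should lie. The stated 85% power is a separate matter that this point does not use: the one-sample arcsine formula gives Φ(0.36 × √20 − 1.645) = 48.6%.

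**Assumptions (not in the documents).** Coding, number of items, and response distributions.

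**Step 1: where the cut lies.**
- Coding 1-6: midpoint (1 + 6)/2 = 3.5. The cut of 3 maps to 100 × (3 − 1)/5 = 40. The benchmark's 50 maps to 3.5.
- Coding 0-5: midpoint (0 + 5)/2 = 2.5. The cut of 3 maps to 100 × 3/5 = 60, stricter than neutral.

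**Step 2: which means are affected under 1-6 coding.** These exceed 3 but not 3.5:
- 1 item: none
- 2 items: 3.5
- 3 items: 3.33
- 4 items: 3.25 and 3.5
- 5 items: 3.2 and 3.4
- 10 items: 3.1 to 3.5

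Example: (3 + 3 + 3 + 4)/4 = 3.25, which maps to 100 × 2.25/5 = 45. Means of 3 or below remain non-responders.

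**Step 3: no preference, independent uniform answers (exact convolution).**

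| Items | P(mean >3), 1-6 | P(mean >3.5), 1-6 | P(mean >3), 0-5 |
|---|---|---|---|
| 1 | 0.500 | 0.500 | – |
| 4 | 0.664 | 0.444 | 0.239 |
| 5 | 0.695 | 0.500 | 0.222 |
| 8 | 0.762 | 0.460 | – |
| 10 | 0.795 | 0.464 | 0.157 |

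**Step 4: correlated answers, 1-6 coding.** Each person has a normally distributed level. Item answers vary around it with SD 1.0 and are rounded to 1-6. For the 3.5 row, between-person SD is 0.3, 0.5, 0.8, 1.0 or 1.3 with 4, 5, 8, 10 or 15 items (25 settings). For the other rows it is 0.5, 0.8, 1.0 or 1.3 with 4, 5, 8 or 10 items (16 settings).

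| True average | Rate with >3 | Rate with >3.5 | Gap, points | Settings at or above 77%: >3 / >3.5 |
|---|---|---|---|---|
| 3.5 | 61-88% | 42-50% | 11-39 | 5 of 25 / 0 of 25 |
| 4.0 | 73-94% | 61-77% | 10-19 | 12 of 16 / 1 of 16 |
| 4.5 | 84-99% | 73-94% | 5-11 | 16 of 16 / 12 of 16 |
| 5.0 | 91-100% | 84-99% | 1-7 | 16 of 16 / 16 of 16 |

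In the 3.5 row, rates at or above 77% occur only with between-person SD of 0.5 or less and 8 or more items. At SD 0.8 or more the rate is 61-71%.

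**Step 5: false success for a no-preference device.** Taking the test as exact binomial with p0 = 0.77 and n = 20: P(X ≥ 18) = 0.128 and P(X ≥ 19) = 0.037, so 19 of 20 responders are needed. The chance of 19 or more by true responder rate p is p^20 + 20(1 − p)p^19:
- 0.61: 0.07%
- 0.69: 0.6%
- 0.71: 1.0%
- 0.76: 3.0%
- 0.84: 15%
- 0.88: 29%
- 0.50 (the most that >3.5 allows in Step 4): 0.002%

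**The case against.** The strongest objection is that the premise is not documented. Nobody working from these documents knows the coding, and 0-5 coding reverses the direction. This stands. A reader might infer that the plan has been shown to overstate the responder rate. It has not: what is established is that the cut is not anchored to neutral, and the overstatement is conditional on 1-6 coding.

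Second, >3 looks like a deliberate choice of the favourable response categories, and calling 3.25 below neutral assumes evenly spaced anchors. This stands in part. The rule is right for one item under 1-6 coding, but Section 10.4.2 averages the items and so already treats the answers as equally spaced numbers.

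Third, the benchmark differs in other ways: it is an average over comfort questions on another scale, and Section 10.2 also presents 77% as a desired proportion. This stands. A reader might infer that >3.5 would make the two quantities comparable; it would align the neutral point only.

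Fourth, the size depends on the assumed distribution. This also stands. The contrast of 12 of 16 against 1 of 16 belongs to a true average of 4.0 and is gone at 5.0, and the plan states no expected mean.

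A reader might also infer that an indifferent population would readily win the trial. With 19 of 20 needed, that chance is small in most settings. It becomes material only where people differ little from one another and the items are many.

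**Conclusion.** The point holds in conditional form, should be fixed, and carries medium confidence. As written, the primary responder rule cannot be checked against neutral, although the benchmark it is compared with was defined by neutral.

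Under 1-6 coding, which fits the text best because >3 is then the favourable half of one item, multi-item means above 3 and up to 3.5 are misclassified as improvement. The cut matters mainly for indifferent or mildly favourable results and little for a clearly preferred device. False success for a no-preference device is at most about 1% at responder rates up to 0.71, but about 15% at 0.84 and 29% at 0.88.

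Under 0-5 coding there is no inflation, and if the form makes 3 the neutral point the rule is sound. Item counts, the item SD of 1.0, the between-person spread and the exact test are all assumptions.

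**What to change.** Before any data are seen:

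- In Sections 1.1, 3, 10.1, 10.2 and 10.4.2, define a responder as a participant whose Design-subsection mean is strictly above the scale midpoint: >3.5 if items are coded 1-6, >2.5 if coded 0-5.
- Print the item coding, the anchors and the number of Design items.
- If the survey form shows that 3 is the neutral point, print that layout and keep >3.
- State in Section 10.2 that this aligns the neutral point with the benchmark but does not make the endpoint identical to it, since the benchmark is an average over comfort questions on another scale.

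Cost: an amendment with IRB approval (Section 13.2) and one definition changed in five places. The survey, visits and data stay the same. Under 1-6 coding the responder rate may be lower, so 77% becomes harder to reach; under 0-5 coding it may be higher.

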4 STUDY DESIGN

4.1 OVERALL STUDY DESIGN

This prospective, single-site IDE study uses an open-label, single-arm, repeated-measures design with participants serving as their own control. One US academic medical center will enroll 20 experienced MED-EL CI users to evaluate the design and usability of the SONNET 3 (EAS) Audio Processor (AP). Participants may enroll before or at Visit 1. Each participant will complete a 3-week trial with the SONNET 3 (EAS) AP. Participants will return 2-4 weeks after Visit 1 to complete a custom survey comparing AP design (Visit 2). Study objectives will assess patient-reported improvement in AP design and compare usability with the SONNET 3 (EAS) AP to participants' existing SONNET (EAS) or SONNET 2 (EAS) AP. The primary endpoint will demonstrate superiority of the SONNET 3 (EAS) AP design compared to the existing AP designs.

4.2 SCIENTIFIC RATIONALE FOR STUDY DESIGN

Randomization is not appropriate for this study. A repeated-measures, within-participant design using participants as their own control enables clinically meaningful comparisons that account for patient heterogeneity.

4.3 END OF STUDY DEFINITION

An individual's participation is considered complete when the participant completes the last visit, or the last procedure shown in the Schedule of Events Table in [7.2.5](#).

5 STUDY ENROLLMENT AND WITHDRAWAL

5.1 PARTICIPANT INCLUSION CRITERIA

Participants must meet all inclusion criteria below:

- Implanted with a MED-EL cochlear implant in at least one ear
- ≥ 12 months since activation of the MED-EL audio processor
- Consistently using a SONNET (EAS) or SONNET 2 (EAS) Audio Processor
- Ability to complete all study procedures
- Participant and parental (if applicable) commitment to comply with all study procedures for the duration of the study

5.2 PARTICIPANT EXCLUSION CRITERIA

Participants must not meet any exclusion criteria below:

- Evidence that hearing loss is retrocochlear in origin

- Unable to provide reliable feedback during cochlear implant programming
- Skin or scalp condition precluding use of the SONNET 3 (EAS) Audio Processor
- Unrealistic participant or parent (if applicable) motivation or expectations
- Participants without a stable fitting map at enrollment e.g., due to changes in hearing, global health status, etc.

5.3 STRATEGIES FOR RECRUITMENT AND RETENTION

The current study aims to enroll 20 participants. Potential participants will be recruited through the outpatient clinics at a single academic medical center. The site may review existing records for patients to determine potential participants. Participants may also be recruited by their clinical audiologists, who will refer the potential participant to the clinical research team to verify candidacy. Parents or legal guardians must provide permission for participants under 18 years of age to participate. The IRB will determine needs and age required for assent. Parental/guardian permission and assent must be explained and signed before enrollment testing.

5.4 PARTICIPANT WITHDRAWAL OR TERMINATION

5.4.1 REASONS FOR WITHDRAWAL OR TERMINATION

Participants or their parents/legal guardians may choose to withdraw from the study at any point during participation. The site principal investigator may terminate an individual's participation in the study for reasons outlined below:

- Noncompliance with the study protocol
- Health concerns that prevent required follow-up procedures or interval visits

The site investigators should report participant withdrawals and terminations to study monitors as soon as possible. Subjects who withdraw prior to completion of Visit 2 will be required to return the SONNET 3 (EAS) Audio Processor to receive compensation for Visit 1. Participants who are considered lost-to-follow-up should also be reported to study monitors immediately. Every effort should be made to contact participants lost-to-follow-up and determine the reason for noncompliance. If the SONNET 3 (EAS) is not returned, the subject's clinical audiologist will be made aware so that efforts can be made to retrieve the study device at a clinical follow-up appointment.

5.4.2 HANDLING OF PARTICIPANT WITHDRAWALS OR TERMINATION

Withdrawn participants will continue to be seen by their clinical audiologist for regular follow-up care, but no additional data will be collected. Participants who sign the informed consent/assent form but do not complete all study intervals may be replaced and will return any study equipment to the site. Baseline data collected on withdrawn subjects who are replaced will not be included in the modified intent-to-treat (mITT) or per population (PP) analysis datasets.

6 STUDY DEVICE

6.1 STUDY DEVICE DESCRIPTION

6.1.1 CLASSIFICATION

[figure not shown]
The SONNET 3 (EAS) Audio Processor is an external component intended for use with the MED-EL Cochlear Implant System, a class III medical device (P000025). All study participants will be experienced MED-EL CI users who have been wearing an FDA-approved SONNET (EAS) or SONNET 2 (EAS) Audio Processor (P000025/S078 and P000025/S112, respectively) for at least 12 months. Details of the SONNET 3 (EAS) classification can be located in the FDA submission P000025/S131 (June 28, 2024).

6.1.2 DETAILS OF MANUFACTURER

The SONNET 3 (EAS) Audio Processor is manufactured by MED-EL Elektromedizinische Geräte GmbH. MED-EL Corporation is the US importer and the sponsor of this clinical trial.

[figure not shown]
6.1.3 GENERAL DESCRIPTION

The SONNET 3 (EAS) is a cochlear implant audio processor designed to capture and transmit acoustic sound to the surgically implanted internal device. The SONNET 3 (EAS) is designed to be worn behind the ear and is comprised of the control unit, battery pack, earhook, microphone cover, DL-Coil, coil cable, and magnet (see diagram from SONNET 3 (EAS)/SONNET 3 (EAS) EAS User Manual³ below).

The SONNET 3 (EAS) is the third generation SONNET processor. It improves upon the previous generations in earhook design, size, and Bluetooth streaming capability. The SONNET 3 (EAS) is lighter in weight (SONNET/SONNET 2: 10.6 g) and shorter (SONNET/SONNET 2: 56.7 mm) than SONNET/SONNET 2 (see SONNET 3 (EAS)³ specifications below).

Dimensions¹¹

Weight¹¹

SONNET 3 for CI: 9.5g (including 2 zinc-air batteries)
SONNET 3 EAS: 9.9g (including 2 zinc-air batteries)

The SONNET 3 (EAS) has more earhook options, including a flexible silicone earhook and a large earhook to accommodate different pinna sizes. Status indicator lights are visible through the earhook, making viewing easier for users and guardians (see below).

The microphone cover is smaller and designed with an easier mechanism for replacement (see below).

The new touch key feature gives users the ability to adjust program or activate 'Standby Mode' simply by tapping the audio processor.

The audio processor is equipped with 2.4 GHz Bluetooth®⁶ wireless technology. This technology allows the audio processor to connect to certain mobile devices wirelessly (smartphone, tablet, etc.).

The SONNET 3 (EAS) processor is intended for use in patients who have been implanted with a MED-EL cochlear implant (SYNCHRONY/SYNCHRONY 2 (PIN), SONATA, MED-EL CONCERT, PULSAR, COMBI40/COMBI40+).

The SONNET 3 (EAS) Audio Processor is programmed with MAESTRO System Software 11⁴ or higher. MAESTRO 11 builds off of previous versions with the following new features and changes:

- Support the programming of SONNET 3 (EAS) and SONNET 3 (EAS) EAS audio processors
- New user interface for the Configuration options dialog
- New dialog for configuration of audio input options with additional options for programming SONNET 3 (EAS) processors
- Allows the configuration of wireless streaming options for SONNET 3 (EAS)

6.1.4 MECHANISMS OF ACTION

The SONNET 3 (EAS) Audio Processor control unit is programmed using MAESTRO 11 System Software or higher. Once programmed, the control unit is powered via the battery pack and worn on the ear. The control unit captures the acoustic signal via processor microphones, then applies dynamic range compression so that the signal can be converted into electrical output. Maplaw adjustments provide additional gain to the input signal to enhance soft speech before the signal is encoded into electrical pulses. Signal processing algorithms are applied to the speech signal, which is converted into an electrical signal and transmitted via the cable-coil to the internal device for auditory sensation.

6.2 STUDY DEVICE CONTROL

6.2.1 ACQUISITION

MED-EL Corporation will provide MAESTRO 11 or higher software and the necessary Activation Key to the site on a standalone laptop via a loaner agreement for study purposes. MED-EL will also provide an allotment of SONNET 3 (EAS) audio processors to the site via a loaner agreement. The site will notify MED-EL of the assigned processor serial number associated with

each participant. At the conclusion of their participation in the study, each participant may choose to keep the SONNET 3 (EAS), at which time the audio processor warranty will be registered and activated in accordance with standard SOPs. When the study is completed, the site will return any unused/returned SONNET 3 (EAS) audio processors and the loaner laptop to MED-EL.

6.2.2 LABELING

Outer packaging on study devices will be labeled with stickers that read: "CAUTION - Investigational Device. Limited by Federal (or United States) law to investigational use."

6.2.3 STORAGE

The study site should store devices labeled for investigational use separately from approved devices for non-study patients. There are no additional requirements for storage of the device.

